9.4 Observation Period for Adverse Events

The observation period for AE (and SAE) reporting in an individual subject will start at the time of giving written informed consent for participation in the current study and finish with the End of Study visit.

If the investigator becomes aware of an SAE that has started after the observation period has finished, and the event is considered to be associated with IgPro20, then this must be reported to CSL.

9.5 Adverse Event Reporting

9.5.1 Adverse Events

At each clinical evaluation, the investigator (or delegate) will determine whether any AEs have occurred. AEs will be recorded in the AE page of the eCRF. If known, the medical diagnosis of an AE should be recorded in preference to the listing of individual signs and symptoms. The investigator must follow up on the course of an AE until resolution or stabilization. If an AE is ongoing after the End of Study visit, the AE will continue to be followed up until resolution, stabilization, or the subject is lost to follow-up. Subjects who drop out of the study due to reasons other than ‘consent withdrawn’ or ‘lost to follow-up’ will be followed up by weekly telephone calls by site personnel for the full duration of their planned study participation, in order to collect information on AEs.

If, during the study period, a subject presents with a preexisting condition that was not noted at the time of study entry, the condition should be retrospectively recorded in the Medical History section of the eCRF.

9.5.2 Adverse Events of Special Interest

Not applicable.

9.6 Serious Adverse Event Reporting

This study will comply with all applicable regulatory requirements and adhere to the full requirements of ICH Topic E2A (Clinical Safety Data Management: Definitions and Standards for Expedited Reporting).

For SAEs occurring during the study, the investigator or delegate will enter all relevant information in the eCRF.

All SAEs that occur during the course of the study, whether or not causally related to IgPro20, must be entered into the eCRF immediately (within 24 h of the investigator becoming aware of the event).

Adverse events occurring in the period between the time the subject gave written informed consent and the first exposure to IgPro20 that meet 1 or more of the seriousness criteria for AEs must be entered into the eCRF in the same manner as other SAEs and will be included in the clinical study database.

Any SAE that occurs after the End of Study visit that is considered to be causally related to IgPro20 must be **reported immediately (ie, within 24 h of the investigator becoming aware of the event) to CSL.**

9.6.1 Requirements for Reporting of Serious Adverse Events

The minimum reporting requirements for reporting of SAEs include:

- Identifiable subject.
- Suspected medicinal product and / or procedure.
- Event term.
- Identifiable reporting source.

In addition, the investigator must:

- Report all SAEs to the relevant Institutional Review Board / Independent Ethics Committee (IRB / IEC) within the timeframe specified by the IRB / IEC.
- Enter follow-up information in the eCRF until the SAE has resolved, or, in the case of permanent impairment, until stabilized.
- Ensure that the causality assessment for all SAEs is entered in the eCRF.

If the minimum requirements for reporting are fulfilled, the investigator should not wait to receive additional information to fully document the event.

In cases of death, the investigator should supply CSL and the IEC / IRB (as applicable) with any additional information as it becomes available (eg, autopsy reports and detailed medical reports).

9.6.2 Unusual Failure of Efficacy (Canadian sites only)

For study sites located **in Canada only**, unusual failure of efficacy is also to be reported to CSL using the same process and requirements as for serious adverse events in order to comply with Health Canada's *Food and Drug Regulations*. The rationale for this is if a health product fails to produce the expected intended effect, there may be an adverse outcome for the patient, including an exacerbation of the condition for which the health product is being used. In cases where the investigator is uncertain whether an adverse event should be considered as a report of unusual failure in efficacy, the adverse event should be treated as such and reported accordingly.

9.7 Other Significant Event Reporting

9.7.1 Medication Compliance

Details of actual doses of IgPro20 administered (ie, volume, location of infusions, infusion rate) will be recorded in the subject eDiary or a back-up paper diary if the eDiary is not available. Once the eDiary becomes available, the data recorded in the back-up paper diary will be transcribed to the eDiary. The back-up paper diary will be retained as a source

document. Any overdose that is considered by the investigator to be medically significant must be reported as an SAE (see [Section 9.6](#)).

9.7.2 Pregnancy and Lactation

A female subject who becomes pregnant while participating in the study, or up to and including 20 weeks after the last study dose of IgPro20, must notify the investigator immediately.

If a female subject becomes pregnant, she must discontinue forced upward titration treatment regimen with IgPro20. Her study participation will be discontinued and the procedure for discontinuation of a subject will be followed, as described in [Section 4.2](#).

This requirement is not because IgPro20 is potentially harmful to pregnant women or the fetus, but because pregnancy is likely to alter IgG metabolism and may result in medical need to adjust the IgPro20 dose, which will affect her ability to follow the forced upward titration schedule.

CSL must be notified within 5 days of the investigator becoming aware of the pregnancy.

Whenever possible, a pregnancy in a subject exposed to IgPro20 should be followed to term so as to assess any potential occurrence of congenital anomalies or birth defects. Any follow-up information, including premature termination and the status of the mother and child after delivery, should be reported by the investigator to CSL using a Pregnancy Reporting / Outcome Form.

9.8 IRB / IEC Reporting Requirements

The time frame within which an IRB / IEC must be notified of deaths and investigational product-related unexpected SAEs is stipulated by each IRB / IEC. It is the investigator's responsibility to comply with the requirements for IRB / IEC notification. CSL will provide investigators with all details of all SAEs reported to regulatory authorities.

9.9 Follow-up of Adverse Events

Every effort should be made to follow-up subjects who continue to experience an AE or an SAE on completion of the study until the AE resolves, is stabilized, or until the subject is lost

to follow-up. Further details on follow-up of subjects who drop out from the study are described in [Section 9.5.1](#). All follow-up information should be entered into the eCRF within 24 hours of awareness and documented in the subject's medical records. Information on attempted follow-up contacts should be documented in the subject's medical records.

If an ongoing AE becomes serious after completion of the study, this information should be sent as follow-up and must be reported immediately (within 24 hours of the investigator becoming aware of the event) to CSL as described in [Section 9.6](#).

All follow-up information (and attempted follow-up contacts) should be documented in the subject's medical records. Details of the subject's progress should also be submitted to CSL Global Clinical Safety and Pharmacovigilance.

10. Assessments

10.1 Subject Characteristics

Subject characteristics to be evaluated will include:

- Demographic data (eg, sex, race).
- Medical and surgical history.
- Details of diagnosis and disease status at enrollment into the study.
- Previous and concomitant therapy.

10.2 Efficacy Assessments

CCI

- **CCI**

10.3 Safety Assessments

Safety will be assessed by:

- The frequency and severity of AEs.
- Local reactions (injection site reactions).
- Tolerability of a certain infusion parameter (ie, percentage of subjects and infusions per cohort by volume/flow rate subgroup experiencing no severe local reactions for each of the infusion parameter levels).
- Physical examination.

- Vital signs.
- Clinical laboratory tests:
 - Biochemistry
 - Hematology

Clinical laboratory tests will be performed at time points as detailed in the [Schedule of Assessments](#). More frequent evaluations may be performed, if clinically indicated, at the discretion of the investigator.

10.4 Pharmacokinetic and Pharmacodynamics

Not applicable.

10.5 Other Assessments

Not applicable.

11. Statistics

11.1 Sample Size Estimation

A minimum of 45 evaluable (15 per cohort) subjects will be needed. This is based on an assumed response rate for reaching the top infusion parameter for each endpoint of 50% (ie, 100 mL/h for the Pump-Assisted Flow Rate Cohort, 50 mL per injection site for the Pump-Assisted Volume Cohort, and 2 mL/min for Manual Push Flow Rate Cohort). Using a binomial distribution with 15 evaluable subjects, there will be a 94% probability that the observed response rate for a single endpoint in the study is $\geq 33\%$.

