Eligible subject	Eligible subjects are subjects meeting the inclusion/exclusion criteria.
Enrolled subject	Enrolled subjects are eligible subjects who freely signed informed consent form and enrolled in the study.
Full Analysis Set	The Full Analysis Set (FAS) will comprise all subjects who provide informed consent and who are included in the study; ie, who undergo study procedures after Screening. Screening failures will not be included in the FAS. However, the number of Screening failures will be summarized in the disposition tables and all Screening failures will be listed.
Safety Population	The Safety Population will comprise all subjects in the Full Analysis Set who received at least 1 dose or a partial dose of IgPro20 in the study.
Treatment-emergent adverse event	Treatment-emergent adverse events are adverse events occurring after the start of the first IgPro20 infusion in the study and up to the End of Study visit.
Pump-Assisted Volume Cohort	Subjects testing volumes per injection site of 25 mL up to 50 mL.
Pump-Assisted Flow Rate Cohort	Subjects testing flow rates per injection site of 25 mL/hour up to 100 mL/hour.
Manual Push Flow Rate Cohort	Subjects testing flow rates per injection site of 25 to 30 mL/hour up to 120 mL/hour (equivalent of approximately 0.5 mL/minute up to 2 mL/minute)

1. Introduction

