3.1 Study Design and Rationale

This multicenter, open-label, parallel-arm, non-randomized study is designed to evaluate safety and tolerability of higher infusion parameters of IgPro20 in subjects with PID. The study will include 3 cohorts with a minimum of 15 subjects each as follows:

- Pump-Assisted Volume Cohort (weekly infusions): Volume per injection site of 25 mL up to 50 mL.
- Pump-Assisted Flow Rate Cohort (weekly infusions): Flow rate per injection site of 25 mL/hour up to 100 mL/hour.
- Manual Push Flow Rate Cohort (2 to 7 infusions per week): Flow rate per injection site of 25 to 30 mL/hour up to 120 mL/hour (equivalent of approximately 0.5 mL/minute up to 2 mL/minute; see [Table 1](#)).

Each cohort will test 3 infusion parameter levels (for Pump-Assisted Flow Rate Cohort – 4) for at least 4 weeks each over a duration of 12 weeks (for Pump-Assisted Flow Rate Cohort – 16 weeks). After the fourth week on each level, qualifying subjects (responders) will switch to the next infusion parameter level (eg, from 25 to 50 mL/h). During the study the weekly dose will remain unchanged (as prescribed by treating healthcare provider, usually within 100-200 mg/kg per week range); only the respective infusion parameter under evaluation will change. If a subject is unable to tolerate the respective infusion parameter level (ie, is a non-responder at that level, for definition see [Section 11.3.5](#)), the subject will continue study

[figure not shown]
participation at the individually previously tolerated infusion parameter level for the remaining full study duration, to collect safety information.

If a subject within the Pump-Assisted Cohort is able to perform ≥ 3 out of 4 (75%) valid infusions at a certain infusion parameter level, he/she will be considered to be a responder for this infusion parameter level (eg, completed 3 infusions with 50 mL/h means responder for 50 mL/h). Valid infusions do not need to be consecutive. Determination of a responder in the Manual Push Cohort is more complex due to the expected variable frequency of infusions per week for different subjects (see [Section 11.3.5](#) for further details). Valid infusions in this cohort also do not need to be consecutive. However, each subject needs to adhere to the same schedule (number of infusions per week) throughout the study.

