An infusion parameter will be considered successfully achieved if at least one third of the subjects in the corresponding cohort (5 of 15) are responders at that infusion parameter level, as defined above. The highest achieved infusion parameter level will be used for the label change. The rationale for this is based on medical experience (personal communications with several key opinion leaders and limited clinical research experience). A response rate for reaching the top infusion parameter for each endpoint of 50% is assumed. Using a binomial distribution with 15 evaluable subjects, there will be a 94% probability that the observed response rate for a single endpoint in the study is $\geq 33\%$.

Excluding the differences in infusion parameters/administration, all 3 cohorts have a similar overall study design (including AE collection). A schematic overview of the study is presented in [Figure 1](#).

Figure 1. Study Overview

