3.5 Planned Number of Subjects

Approximately 50 subjects will be enrolled into the study. A target of 45 evaluable subjects (ie, 15 subjects per cohort) is needed. Enrolled subjects will include a target of 14 (30%) pediatric subjects ≤ 17 years of age and a target of 9 (20%) obese subjects with BMI of ≥ 30

kg/m². Pediatric and obese subjects may be distributed across any or all of the treatment cohorts without respect to balanced enrollment within the cohorts for these subpopulations..

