4.2.3 Replacement Policy

Subjects withdrawn from the study will not be replaced.

5. Study Interventions

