11.2.2 Safety Population

The Safety Population will comprise all subjects in the Full Analysis Set who received at least 1 dose or a partial dose of IgPro20 in the study.

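### The 94% chance of meeting the 33% criterion is stated for 15 undefined evaluable subjects, while the criterion divides by all dosed subjects

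*Protocol*

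**What the plan says.** Protocol 11.1 assumes a 50% response rate at the top level of each cohort and continues: "Using a binomial distribution with 15 evaluable subjects, there will be a 94% probability that the observed response rate for a single endpoint" is at least 33%. Protocol 3.1 and SAP 4.5 give the same statement. Protocol 3.1 words the rule as success if "at least one third of the subjects in the corresponding cohort (5 of 15) are responders" at that level.

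The analysis sections use a different set. Under Protocol 11.3.5 d) and SAP 11.1, the response percentage R_c,p is the number of responders divided by the number of Safety Population (SAF) subjects in the cohort, and success means R_c,p of at least 33%. Protocol 11.2.2 defines the Safety Population as "all subjects in the Full Analysis Set who received at least 1 dose or a partial dose of IgPro20 in the study". SAP 8.1.1 keeps subjects with a missing outcome in the denominator.

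On numbers, Protocol 3.1 says: "The study will include 3 cohorts with a minimum of 15 subjects each as follows". Protocol 3.5 says: "Approximately 50 subjects will be enrolled into the study. A target of 45 evaluable subjects (ie, 15 subjects per cohort) is needed". Protocol 4.2.3 says: "Subjects withdrawn from the study will not be replaced".

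The protocol defines a Full Analysis Set and a Safety Population, and the SAP adds a Screened Analysis Set. Neither document defines an evaluable subject.

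**The concern.** The probability is computed on one population and the decision is taken on another. The two coincide only if the dosed subjects of a cohort are exactly the 15 evaluable ones. The plan sets 15 as a minimum and enrols a margin above it, so a dosed cohort larger than 15 is possible. One extra dosed subject raises the number of responders required from 5 to 6.

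The plan also does not say outright whether the assumed 50% refers to dosed subjects, with dropouts counted as failures, or to evaluable subjects only.

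There is no formal testing. The 94% is therefore the only operating characteristic offered for the rule that picks the top infusion parameter to recommend for the label, and the only quantitative support for 15 per cohort. It should describe the rule as it will be applied.

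**Working it through.** **Inputs.** True top-level response rate 50% and 15 evaluable subjects per cohort (Protocol 11.1, SAP 4.5). Criterion R_c,p ≥ 33% with all Safety Population subjects in the denominator (Protocol 11.3.5, SAP 11.1). About 50 enrolled for 45 evaluable (Protocol 3.5). No dropout rate is stated.

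**Formula.** For n dosed subjects the number of responders needed is r = ceil(0.33 × n). For n from 15 to 20, ceil(n/3) gives the same r, so the 33% and one-third wordings agree. The probability of success at a true 50% is 1 − [C(n,0) + … + C(n,r−1)] / 2^n.

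**The plan's own figure.** n = 15, r = 5: 1 − (1 + 15 + 105 + 455 + 1365)/32768 = 1 − 1941/32768 = 0.9408. The stated 94% is reproduced.

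**Size of the margin.** (50 − 45)/50 = 10%. An even split of 50 gives 50/3 = 16.7, so 16 to 17 per cohort if nearly all are dosed. The even split and the dosing of nearly all are both assumptions.

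**Responders needed.** 5/16 = 31.3% and 5/17 = 29.4% both fail; 6/16 = 37.5% and 6/17 = 35.3% pass.

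**Probability by dosed cohort size, 50% of all dosed:**

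| Dosed | Needed | Ways to fall short / 2^n | Probability of success |
|---|---|---|---|
| 15 | 5 | 1941 / 32768 | 94.1% |
| 16 | 6 | 6885 / 65536 | 89.5% |
| 17 | 6 | 9402 / 131072 | 92.8% |
| 18 | 6 | 12616 / 262144 | 95.2% |
| 19 | 7 | 43796 / 524288 | 91.6% |
| 20 | 7 | 60460 / 1048576 | 94.2% |

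The risk of missing the criterion is 5.9% at 15, 10.5% at 16 and 7.2% at 17.

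**Extra subjects dosed but unable to respond.** With 16 to 18 dosed, 6 are needed. If only 15 can respond, each with probability 50%, success has probability 1 − (1941 + 3003)/32768 = 1 − 4944/32768 = 0.8491, or 84.9%.

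**The case against.** The strongest reply is that enrolled does not mean dosed. The protocol's definition reads: "Enrolled subjects are eligible subjects who freely signed informed consent form and enrolled in the study". That rules out counting screening failures in the margin, but it does not put the margin after the first dose. Screening runs from Day −35 to Day −7, and eligibility is reviewed again on Day 1, when the first infusion is given. A subject can be lost in between and never enter the Safety Population. If the step from 50 to 45 covers such losses and 15 per cohort are dosed, 94% is correct on the plan's own denominator. This stands: a reader might infer that about 50 enrolled must mean 16 to 17 dosed per cohort, but the documents do not say so.

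A reader might also infer that the figure holds only at exactly 15 dosed, or that larger cohorts always do worse. Neither is true, because the required count moves in steps. No even split is prescribed, and a 15/15/20 split of 50 would give 94.1%, 94.1% and 94.2%.

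Lower figures can be built by taking the 50% as a rate among evaluable subjects and losing the whole 10% at random after dosing. The rate among dosed subjects is then 45%, and the probability 80.2% at 16 or 85.3% at 17. This stacks assumptions. The plan's 50% is a rate for reaching the top level and, in Protocol 11.3.5, a subject's probability of being a responder. Read naturally, an early dropout is already a non-responder. The 84.9% case also needs all the extra subjects to be dosed and then unable to respond.

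Finally, the decision rule is explicit and consistent between protocol and SAP, so 5 of 16 could not pass by mistake, and the SAP says that the sample size does not rest on hypothesis testing. That limits the weight of the point. It does not remove the mismatch between the population behind the stated probability and the one used for the decision.

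**Conclusion.** The point holds as a population mismatch in a stated operating characteristic, of minor to moderate severity. It is not an arithmetic error: a reader might infer that the 94% was miscalculated, but it reproduces exactly for 15 subjects.

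The size depends on facts that the plan leaves open. With 15 dosed per cohort there is no change. With 16 or 17 dosed and the 50% taken over all dosed subjects, the probability is 4.6 or 1.3 points below 94.1%. If the subjects beyond 15 are dosed but cannot respond, it is about 9 points lower. At 18 or 20 dosed, with the 50% over all dosed, it is at or slightly above the stated figure.

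**What to change.** Change the wording in Protocol 3.1 and 11.1 and in SAP 4.5:

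- Replace the evaluable subjects with the Safety Population (SAF), the set that the criterion uses.
- State that the assumed 50% is of all dosed subjects, with dropouts counted as non-responders.
- Replace the single 94% with the probability and the responders needed for each dosed cohort size from 15 to 20, as in the table above. Add that it is 84.9% if 16 to 18 are dosed and only 15 can respond.
- In Protocol 3.1, label the 5-of-15 count as the 15-subject case of the one-third rule.

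Given by dosed cohort size, the statement is right whatever the enrolment margin turns out to cover. The cost is text only, and the stated figure may look slightly less favourable than 94%. Enrolment, the minimum numbers of valid infusions (k), the 33% criterion and the escalation scheme do not change.

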11.2 Description of Analysis Datasets

11.2.1 Full Analysis Set

The Full Analysis Set (FAS) will comprise all subjects who provide informed consent and who are included in the study; ie, who undergo study procedures after Screening. Screening failures will not be included in the FAS. However, the number of Screening failures will be summarized in the disposition tables and all Screening failures will be listed.

11.2.2 Safety Population

The Safety Population will comprise all subjects in the Full Analysis Set who received at least 1 dose or a partial dose of IgPro20 in the study.

11.3 Statistical Analyses and Methods

A complete description of the statistical analyses and methods will be available in a Statistical Analysis Plan, which will be finalized before the database is locked.

11.3.1 Subject Disposition and Characteristics

11.3.1.1 Subject Disposition

The number of subjects who were screened, enrolled into the study, and completed the study will be presented in summary tables by treatment group and total subjects. The reason for discontinuing the study product or withdrawing a subject from the study will be listed by subject.

11.3.1.2 Subject Characteristics

At a minimum, subject characteristics will be presented in summary tables. Continuous data will be summarized by descriptive statistics (number of observations, mean, standard deviation, minimum, maximum, median, Q1, Q3) and categorical data will be summarized by frequency distributions. Age will be described as both a continuous and a discrete variable. Supportive data will be listed by subject.

